##### **4.3.2.1 Satralizumab and Placebo: Double-blind Period**

The patient will receive an SC injection of satralizumab or placebo at Weeks 0, 2 and 4, and Q4W thereafter during the double-blind period. The double-blind period ends when either the patient has a relapse or the total number of protocol-defined relapses judged by the CEC reaches 26.

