**Figure 2 Assessment of a Relapse**

The sequence of procedures of the extra visit at relapsing should be as follows:

- a. The assessment at the extra visit at relapsing, which is listed in [Appendix 1](#), is performed, where the EDSS/FSS is assessed by examining assessor.
  - i. If the symptom is of a clinical relapse as judged by Investigator, study drug should not be administered until the patient enters extension period.
- b. The symptom is confirmed whether it meets the criteria for a protocol-defined relapse.
- c. The Relapse Assessment Form will be completed and sent to the CEC (Please see [Section 4.5.3.3](#)).
- d. Rescue therapy should proceed at the discretion of the treating Investigator (the sequence may be different in case of an emergency).

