### **4.5.3.3 Reporting a Potential Relapse to the CEC**

The Relapse Assessment Form will be sent (e.g., by fax, e-mail) immediately, together with the EDSS/FSS scoring sheets for the current visit, the most recent EDSS/FSS assessment visit, and necessary data (if any) to PAREXEL. This should be done regardless of the assessment of the site staff about whether the potential relapse meets protocol-defined relapse and regardless of the time when the EDSS/FSS assessment was performed.

During the double-blind period, the form and the data will be reviewed by the CEC. The CEC will review according to the CEC charter, and will be able to request additional information to assist in the determination of a relapse if necessary.

If the CEC considers that the protocol-defined relapse has been met, the patient should be withdrawn from the double-blind period and can enter the extension period even if Investigator considers that no protocol-defined relapse has occurred.

Details regarding the CEC responsibilities and the process of adjudication are described in the Section 3.1.4 and CEC charter.

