### **6.1 ANALYSIS POPULATIONS**

#### **6.1.1 Efficacy Analysis Populations**

The intent-to-treat (ITT) population will serve as the primary population for the analysis of efficacy, which consists of all randomized patients in the double-blind

period in the study. Patients will be analyzed as randomized for analysis purposes in the ITT.

The Per-Protocol Set (PPS) will include all patients in the ITT population who received at least 3 doses of study drug, and without any major protocol deviations which are considered to have an impact on efficacy. Patients will be analyzed as treated for analysis purposes in the PPS.

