4.1 Overall Study Design and Plan

This is a multicenter, randomized, addition-to-baseline treatment, double-blind, placebo-controlled, parallel assignment study followed by an open-label extension period. Subjects will be randomized to either SA237 120 mg or placebo. Blinded study drug will be administered subcutaneously (SC) at Weeks 0, 2 and 4, and thereafter every 4 weeks (Q4W) in combination with one of the following baseline maintenance treatments: azathioprine, mycophenolate mofetil or oral corticosteroids (treatment with both oral

corticosteroids and either azathioprine or mycophenolate mofetil will be accepted in subjects aged 12 to 17 years at the time of informed consent). The randomization will be stratified by baseline annual relapse rate (ARR) and geographic region (Asia and European (EU)/Other). The primary efficacy endpoint is the time to first relapse (TFR) based on protocol-defined relapse, where the time point of relapse onset is defined as the time at which the subject experiences any new or worsening neurological NMO representing clinical symptom(s). The duration of the study will depend on the relapse rate, since the double-blind period of the study will end when the total number of protocol-defined relapses judged by Clinical Endpoint Committee (CEC) reaches 26 while the extension period is expected to last until Last Observation Visit.

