5.5 Analysis Populations

The intent-to-treat (ITT) population will serve as the primary population for the analysis of efficacy, which consists of all randomized subjects. Subjects will be analyzed as randomized for analysis purposes. In case even a subject is incorrectly stratified at time of randomization, the analysis will be performed using the stratification for randomization.

The Per-Protocol Set population (PPS) will include all subjects in the ITT population who received at least 3 doses of study drug, and without any major protocol deviations which are considered to have an impact on efficacy. Subjects will be analyzed as treated for analysis purposes in the PPS.

The Safety Set (SAF) population will include all randomized subjects who have received at least one dose of active study drug or placebo. Subject will be included in the treatment group corresponding to the trial treatment they actually received for the analysis of safety data using the SAF population, i.e. patients who received at least one dose of SA237 will be assigned to the SA237 treatment arm, irrespective of randomized arm. .

The All-Subjects-Treated (All SA237) population will be defined as all enrolled subjects who took at least one dose of active study drug at any time. Date of the first active study drug administration will be defined as Day 1 for All SA237 analysis (i.e. Day 1 of subjects allocated in placebo group is redefined on the day of first dose of SA237 when entering extension period.

The Pharmacokinetics Per-Protocol Set (PK-PPS) and immunogenicity (anti-SA237 antibody; ADA) will include all subjects in the SAF with at least 1 valid post-dose concentration result with a dosing record and sampling time. Pharmacodynamics variables will be analyzed using the SAF population.

The Adolescents population will be defined as all enrolled subjects from 12 to 17 years old (< 18 years) at the first informed consent. After the total number of protocol-defined relapses judged by the CEC reaches 26, the recruitment period for the adolescents may be continued in the extension period until a minimum of 8 adolescents are enrolled into the study.

The following summary and listing will be provided:

- A summary of analysis populations, including the number and percentage of subjects in the defined analysis sets by treatment group and overall.

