5.9 Treatment Compliance

Compliance will be computed by determining the number of SC injections relative to the number of SC injections that should have been administered. The compliance will be evaluated during the double-blind period. If a subject who experience a relapse which is treated with rescue therapy and/or a protocol-defined relapse which is adjudicated by CEC or early discontinued from study treatment, the number of planned and actual SC will be counted based on the visits before the discontinuation. Treatment compliance will be summarized in terms of compliance based on the Safety population. Administration using prefilled syringe will be flagged in the listing of administration.

Compliance will be calculated using the following formula:

$$\text{Compliance (\%)} = \frac{\text{Number of SC injections during the double-blind period}}{\text{Number of planned SC injections during the double-blind period}} \times 100$$

The following summaries and listings will be provided:

- A summary table of compliance will be presented by treatment group, and overall. The number and percentage of treatment compliance will also be presented by categorized compliance as: <80%, 80%-100%, >100%,
- A by-subject listing of study drug administration as well as overall compliance during the double blind and whole period.

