5.10.2 Primary Efficacy Variable

The primary efficacy analyses will be based on the ITT population. Supportive evaluations will be performed using the PPS population.

The primary efficacy endpoint is TFR based on protocol-defined relapses confirmed by the CEC with EDSS/FSS assessment performed by the examining assessor within 7 days after relapse symptoms were reported to site by the subject. TFR is defined as the time from the date of the randomization until the first occurrence of relapse throughout the study. Time point of relapse onset is defined as time at which the subject experiences any new or worsening neurological NMO representing clinical relapse(s) which is later confirmed by the CEC as protocol-defined.

Censor is defined as the earliest day of 1) the end of double blind period for efficacy analysis, 2) switching or increasing the baseline treatment (for details on the identification of the switch and increase in baseline therapy see appendix 7.4), or 3) receiving rescue therapy for clinical relapse.

The primary analysis of the study is to test the equality of the TFR distribution based on protocol-defined relapse in the SA237 + baseline treatment (SA237) and Placebo + baseline treatment (placebo) arms:

$$H_0: TFR_{SA237} = TFR_{\text{placebo}} \text{ versus } H_1: TFR_{SA237} \neq TFR_{\text{placebo}}$$

A stratified two-sided log-rank test using strata of baseline ARR (one vs. more than one) and geographical region (Asia and EU/Other) will be used.

The Kaplan-Meier method will be used to estimate the TFR based on protocol-defined relapses distribution for each treatment group. The Kaplan-Meier curve will provide a visual description of the differences across treatment groups. In addition, estimates of the treatment effect will be expressed as hazard ratio and 95% CIs using a stratified (baseline ARR and geographical region) Cox proportional-hazards model (Exact method will be used for tie data). Treatment by covariate interactions will be assessed by including the pairwise interaction terms in the Cox proportional-hazards model.

The following summary tables, figures and analysis will be provided for the ITT and PPS:

- A summary table of Kaplan-Meier estimate of TFR (protocol-defined relapse) will be presented by treatment group.
- A figure of Kaplan-Meier estimate of TFR (protocol-defined relapse) will be presented by treatment group.
- Analysis of TFR (protocol-defined relapse) will be performed using the stratified log-rank test.

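### The per-protocol set's three-dose rule excludes adherent patients who relapse before the third dose, and does not say which period's doses count

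*SAP*

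**What the plan says.** **Who is in the set.** SAP 5.5 defines the PPS as a set that "will include all subjects in the ITT population who received at least 3 doses of study drug" and has no major deviation judged to affect efficacy. Protocol 6.1.1 agrees: it "will include all patients in the ITT population who received at least 3 doses of study drug". Neither text limits the doses to the double-blind period or makes an exception for relapse.

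**When the third dose falls.** SAP 4.1: "Blinded study drug will be administered subcutaneously (SC) at Weeks 0, 2 and 4". Protocol Appendix 1, Table 6 puts Week 4 at study Day 29 with a window of ±3 days.

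**What a relapse does to dosing.** Under Figure 2 in Protocol 4.5.3.2, once the investigator judges that there is a clinical relapse, "study drug should not be administered until the patient enters extension period". Protocol 4.3.2.1 adds: "The double-blind period ends when either the patient has a relapse" (or when the 26th adjudicated relapse is reached). Under Protocol 4.5.3.3, if the CEC confirms a protocol-defined relapse, "the patient should be withdrawn from the double-blind period and can enter the extension period".

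**How compliance is counted.** SAP 5.9 says that for patients who relapse or stop early, "the number of planned and actual SC will be counted based on the visits before the discontinuation".

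**What the set is for.** SAP 5.10.2: "Supportive evaluations will be performed using the PPS population". It repeats the Kaplan-Meier, stratified log-rank and stratified Cox analyses of time to first relapse (TFR) in the PPS, with time still running from randomization. SAP 5.4.2 uses the choice of population to judge whether the efficacy results are robust to major deviations.

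**The concern.** A per-protocol set is meant to keep patients who followed the protocol. Take a patient dosed at Weeks 0 and 2 who relapses on Day 20. The protocol itself then stops blinded dosing, so the third double-blind dose cannot be given. The patient has deviated from nothing, but leaves the PPS because of the outcome being analysed, and the primary-endpoint event leaves too.

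If extension doses counted instead, the same patient could come back into the PPS by starting open-label satralizumab. Inclusion would then depend on what happened after the event. Both readings select on the outcome, and the text does not choose between them.

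At stake is the value of the PPS as a robustness check. A difference from ITT could reflect deleted events, and agreement with ITT could hide a weaker early effect.

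**Working it through.** **Inputs (SAP 5.14).** Two-sided log-rank test, 5% level, 80% power; hazard ratio 0.335; placebo hazard 0.4184 per year, so satralizumab 0.4184 × 0.335 = 0.1402; 70 patients, 1:1; 10% dropout over 2 years; 1 year of accrual plus 1.5 years of follow-up; 26 events.

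**The plan's own figure.** The Schoenfeld formula gives (1.960 + 0.842)² / (0.25 × ln(0.335)²) = 26.25 events. Power with 26 events is 79.6%, so 26 is reproduced. Expected events from 70 patients are 27.0 with uniform accrual and 25.5 with linearly rising accrual, also consistent.

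**Events before the third dose.** Dose 3 is due 28 days after dose 1.
- Placebo: 35 × (1 − exp(−0.4184 × 28/365.25)) = 35 × 3.16% = 1.10.
- Satralizumab: 35 × (1 − exp(−0.1402 × 28/365.25)) = 35 × 1.07% = 0.37.
- Total 1.48, or 5.7% of 26. Across the dosing window (25 to 31 days) the total is 1.3 to 1.6.
- Chance of at least one: 1 − exp(−35 × (0.4184 + 0.1402) × 28/365.25) = 78%.
- With about 24.5 events left, power falls from 79.6% to 77.3%.

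**Kaplan-Meier rates.** Conditioning on 28 relapse-free days moves the 1-year relapse-free rate from 65.8% to exp(−0.4184 × (1 − 28/365.25)) = 68.0% on placebo, and from 86.9% to 87.9% on satralizumab.

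**Hazard ratio.** Simulated with 35 per arm, uniform accrual and 10% two-year dropout. The PPS drops anyone whose relapse or dropout comes before 28 days. The first, second and fourth rows use 600 trials per scenario, followed to 2.5 years. Everything about the early period beyond proportional hazards is an assumption.

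| First 4 weeks | Median HR, ITT | Median HR, PPS |
|---|---|---|
| Same HR, 0.335 | 0.34 | 0.34 |
| No effect (assumption) | 0.36 | 0.33 |
| No effect, hazard doubled (assumption) | 0.41 | 0.33-0.34 |
| No effect, hazard tripled (assumption) | 0.44 | 0.34 |
| No effect, hazard ×4 (assumption) | 0.49 | 0.33 |

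Cutting instead at the 26th event (4,000 trials) gave 0.37 against 0.33 for the second row; another run gave 0.36 against 0.32. The third and fifth rows come from the set-up that cuts at the 26th event. In the tripled-hazard case about 6.5 events are removed.

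**Compliance against the PPS.** Under SAP 5.9 the Day-20 relapser has 2 planned and 2 actual injections: 2/2 = 100%. Under SAP 5.5 the same patient has 2 doses, fewer than 3, and is excluded.

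**The case against.** The strongest reply is that little rests on this set. ITT is the primary population and keeps every early relapse. The gatekeeping and the five TFR sensitivity analyses use ITT, and no decision rule uses the PPS. SAP 5.5 also requires a listing of each patient's reason for exclusion, so the losses would be visible. All of this stands, and it limits the seriousness of the point.

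A reader might infer more than the documents support in three ways.

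- *That the PPS hazard ratio is biased towards satralizumab.* Under the plan's own proportional hazards it is not. Bias needs a delayed effect, which the documents neither state nor exclude. Even 0.37 against 0.33 is ln(0.37/0.33) = 0.11 on the log scale, beside a standard error of roughly 2/√26 = 0.39. The fourfold scenario is extreme: it implies 70 × (1 − exp(−4 × 0.4184 × 28/365.25)) = 8.4 relapses within 28 days. Entry requires 8 weeks on stable baseline treatment, and a relapse during screening is a screen failure, which makes such an early excess less plausible.
- *That everyone in the PPS is relapse-free for 4 weeks by construction.* Dosing stops when the investigator judges a relapse, but onset is dated to first symptoms and the CEC may confirm an event that the investigator did not consider protocol-defined. Such a patient can receive dose 3 after onset and stay in. The window also allows dose 3 from Day 26.
- *That the exclusions must be common, because SAP section 1 dropped a logistic regression on account of many early events.* It does not define early, and relapse-free rates are analysed every 24 weeks. The remark does not show events before Week 4.

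It can also be said that the wording does not bar extension doses, so an early relapser might remain in the set. That is true of the literal text, but it replaces one outcome-dependent rule with another, and the figures above would then not apply.

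**Conclusion.** The rule is wrong as written, with a limited effect. Counting double-blind doses, it excludes adherent patients because they relapsed, contrary to how SAP 5.9 counts adherence. Counting extension doses, it makes inclusion depend on treatment after the event.

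The ITT primary analysis is untouched. In the supportive PPS analysis, at the planning hazards with dose 3 on schedule, about 1.5 of 26 events are expected to be lost, roughly three on placebo for each one on satralizumab. The 1-year relapse-free rate rises by about 2 percentage points on placebo and 1 on satralizumab. The hazard ratio is essentially unchanged under proportional hazards. It is biased in favour of satralizumab only if the effect is delayed; assuming no effect for 4 weeks, it is about 0.36-0.37 in ITT and 0.32-0.33 in the PPS. The documents do not establish that delay or its direction, so no bias should be asserted, only that this PPS cannot rule out a weak early effect.

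**What to change.** In SAP 5.5 and Protocol 6.1.1, replace the dose criterion with: *received all double-blind doses scheduled up to the earliest of the third dose, the relapse (investigator-judged or CEC-confirmed) that ended double-blind dosing, and the clinical cut-off*. This names the period, follows the logic of SAP 5.9, and covers both routes by which dosing ends. Report by arm any early relapsers whose PPS status changes.

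The wording also excludes a patient who missed one of the first three scheduled doses but later reached three. If that is not intended, keep the present minimum, limit it to double-blind doses, and add only the exception for relapse and cut-off.

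The cost is one sentence in each document and a rerun of the PPS tables. Dosing, visits, blinding and the primary analysis do not change. The PPS hazard ratio may become slightly less favourable. Protocol 1.3 reports the double-blind period as complete, so a change made now should be labelled post hoc and shown beside the result under the existing rule.

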5.6 Demographic and Other Baseline Characteristics

Summary tables and listing will be provided as follows for ITT, PK-PPS and SAF:

- Demographics will be summarized as collected at screening or baseline visit before administration of first dose of study drug and will include gender, race (American Indian/Alaska Native, Asian [Japanese], Asian [Non-Japanese], Black/African American, Native Hawaiian/other Pacific Islander, White and Other), Geographic region (Asia, Europe/other), age (years), age category (<18, ≥18), ethnicity, racial subgroup, height, body weight (the first and the third quartiles of body weight will be presented), body mass index (BMI, kg/m²), BMI category (<18.5, ≥18.5 to <25, ≥25 to <30, and ≥30 kg/m²), Baseline ARR (1, >1) , AQP4 status at screening (positive, negative), Diagnosis (NMO, NMOSD) and Baseline treatment (azathioprine, mycophenolate mofetil, oral corticosteroids, azathioprine + oral corticosteroids, mycophenolate mofetil + oral corticosteroids) by treatment group and overall.

- A by-subject listing of demographic data.

Age will be calculated as the number of complete years between a subject's birth date and the date of the first informed consent.

The subgroup summary tables will be presented for ITT and SAF by the defined variables with the exception of ADA status (See section 5.5).

5.7 Medical History

Medical history will be classified according to the terminology of the latest version of the Medical Dictionary for Regulatory Activities (MedDRA).

Medical conditions are categorized as past or concomitant as follows:

- Past diseases: Medical conditions which are specified as start date is before Day 1 Visit date with no ongoing status or the stop date is prior to Day 1 Visit date
- Baseline diseases: Medical conditions which are specified as start date is before Day 1 Visit date with ongoing status or the stop date is on or after Day 1 Visit date.

The following summaries will be provided by treatment group and overall, based on the SAF.

- A summary table of past diseases will be presented by system organ class (SOC) and preferred term (PT).
- A summary table of concomitant diseases will be presented by SOC and PT, by treatment group and overall.
- A by-subject listing of medical history data will be provided.

5.8 Prior and Concomitant Medications

Prior and concomitant medications will be coded using the World Health Organization Drug Dictionary (WHO-DD).

Medication start and stop dates will be compared to the date of the first dose of randomized study drug and thus the medications will be classified as Prior or Concomitant.

Medications that start and stop prior to the date of first dose of study drug will be classified as Prior medications. Medications taken on or after (including ongoing) the first dose of study drug will be classified as Concomitant medication. If a medication starts before the date of first dose of study drug and stops on or after the date of first dose of study drug then the medication will be classified as both Prior and Concomitant medication. NMO/NMOSD pain drugs will be reported as collected on the CRF.

The following summaries will be provided by treatment group and overall, based on the Safety population.

- A summary table of Prior Medications (other treatments than NMO/NMOSD) will be provided by anatomical therapeutic chemical (ATC) and PT.
- A summary table of Concomitant Medications (other treatments than NMO/NMOSD) will be provided by ATC and PT.
- A summary table of Prior NMO/NMOSD drugs for relapse prevention will be provided by ATC and PT.
- A summary table of Concomitant NMO/NMOSD drugs for relapse prevention will be provided by ATC and PT.
- A summary table of Prior NMO/NMOSD drugs for relapse/rescue therapy will be provided by ATC and PT.

- A summary table of Concomitant NMO/NMOSD drugs for relapse/rescue therapy will be provided by ATC and PT.
- A summary table of Prior NMO/NMOSD pain drugs will be provided by ATC and PT.
- A summary table of Concomitant NMO/NMOSD pain drugs will be provided by ATC and PT.
- A summary table of Prior other NMO/NMOSD drugs will be provided by ATC and PT.
- A summary table of Concomitant other NMO/NMOSD drugs will be provided by ATC and PT.
- A by-subject listing of Prior medication data will be provided for NMO/NMOSD pain drugs and others separately.
- A by-subject listing of concomitant medication data will be provided.

